1. PROTOCOL SUMMARY

1.1. Synopsis

Not Applicable.

1.2. Schema

Not Applicable.

1.3. Schedule of Activities (SoA)

The SoA table provides an overview of the protocol visits and procedures. Refer to the [STUDY ASSESSMENTS AND PROCEDURES](#) section of the protocol for detailed information on each procedure and assessment required for compliance with the protocol.

The investigator may schedule visits (unplanned visits) in addition to those listed in the SoA table, in order to conduct evaluations or assessments required to protect the well-being of the participant.

Visit Identifier ^a	Screening ^b		Day -1	Day 1	Day 2	Day 3	Day 4	Day 5	Day 6	Day 7	Day 8	Day 9	Day 10	Day 11	Follow-up		Early Termination/Discontinuation (DC)	
	Day -28 to Day -2	28-35 Days ^c																
Days Relative to Day 1	S1	S2																
Informed consent	X																	
Admission to CRU			X															
Confinement to CRU			X	→	→	→	→	→	→	→	→	→	→	X				
Inclusion/exclusion criteria	X		X															
Medical history	X		X															
Demography ^d	X																	
Physical examination ^e	X		X					X						X				X
Height and weight assessment ^f	X		X		X			X						X				
Safety laboratory tests (blood and urine) ^g	X	X ^h	X		X ^h			X						X				X
eGFR assessment ⁱ	X	X	X		X			X						X				
Quantiferon [®] -TB Gold Test or PPD skin test ^j	X																	
Illegal drug/Tobacco/alcohol use	X		X															
Urine alcohol test or alcohol breath test	X		X															
Urine or serum pregnancy test (WOCBP only)	X		X											X				X
Contraception check ^k	X		X											X	X			X

Visit Identifier ^a	Screening ^b		Day -1	Day 1	Day 2	Day 3	Day 4	Day 5	Day 6	Day 7	Day 8	Day 9	Day 10	Day 11	Follow-up	Early Termination/ Discontinuation (DC)
	Day -28 to Day -2	S2														
	SI	S1														
Days Relative to Day 1																
Serum FSH in post-menopausal females amenorrheic ≥12 months and under 60 years of age	X															
Urine drug screen	X		X													
Single supine 12-Lead ECG	X		X											X		X
Vital signs (supine BP, pulse rate) and temperature	X			X				X						X		X
HIV, HBsAg, HBcAb, HCVAb testing ¹	X															
IP administration				X				X		X	X	X	X			
Plasma PK for PF-06651600										X	X	X	X			X ^{nb}
Urine PK for PF-06651600													X			
Genomic banked biospecimens Prep D1 ⁿ			X													
Prior/concomitant treatments	X		X											X		X
CRU discharge														X		
Serious and nonserious adverse event monitoring	X		X											X		X

Abbreviations: → = ongoing/continuous event; BP = blood pressure; DC = discontinuation; eGFR = estimated glomerular filtration rate; HBcAb = hepatitis B core antibody; HBsAg = hepatitis B surface antigen; HCVAb = hepatitis C antibody; HIV = human immunodeficiency virus; CRU = clinical research unit; ECG = electrocardiogram; FSH = follicle-stimulating hormone; IP = investigational product; PK = pharmacokinetic; PPD = purified protein derivative; QFT-G = QuantiFERON[®]-TB Gold; : S1 = Screening Visit 1; S2 = Screening Visit 2; WOCBP = women of childbearing potential.

Visit Identifier ^a	Screening ^b		Day -1	Day 1	Day 2	Day 3	Day 4	Day 5	Day 6	Day 7	Day 8	Day 9	Day 10	Day 11	Follow-up	Early Termination/ Discontinuation (DC)
	Day -28 to Day -2	Day -2														
Days Relative to Day 1	S1	S2														

- a. Day relative to start of study treatment (Day 1).
- b. Screening will consist of 2 CRU outpatient visits (Screening Visits 1 and 2) between 3 to 14 days apart, with the 1st screening visit occurring within 28 days prior to IP administration (Day 1). The 2nd screening visit is only to demonstrate stable renal function with difference between eGFRs at Screening visit 1 (S1) and Screening visit 2 (S2) required to be $\leq 25\%$ of the value obtained at S1. If participant meets all screening criteria at S2 visit, and Day -1 visit can be performed immediately, the participant may be admitted to the unit at conclusion of S2 visit. Other screening procedures completed during the first visit do not need to be repeated. See [Section 4.1](#) for outpatient visit screening schedule.
- c. Contact may occur via telephone contact and must occur 28 to 35 days from administration of the final dose of investigational product.
- d. Demographics will include race, age and gender.
- e. Full physical exam at screening, Day 11, and early termination. Limited physical exam at Day -1 and Day 5 and any time point as deemed necessary by the investigator.
- f. Height to be obtained at S1 only, weight to be obtained at S1, S2 and Days -1, 2, 5, 8 and 11.
- g. Safety laboratory assessments include chemistry, hematology and urinalysis (and microscopy, if needed) and will be performed at S1, on Day -1, Day 5, Day 11 and early termination day. All the assessments must be collected following at least a 4 hour fast.
- h. Serum creatinine only will be assessed on S2 and on Day 2 and Day 8 for eGFR assessment.
- i. To confirm eligibility, participants must have stable renal function defined as $\leq 25\%$ difference for eGFR values at S2 compared to the value at S1. The average of the 2 screening eGFR values will be used for participant stratification and group assignment (provided stable renal function is still demonstrated). If the renal function stability criterion is met but the renal function classification category changes between S1 eGFR and the average of the S1 and S2 eGFRs, the eGFR measurement at Day -1 will also be used to determine the appropriate group classification category using an average of all 3 eGFR values, to determine whether the participant will be eligible for enrollment. The eGFR value will also be determined on Day 2, 5, 8, and 11, and the average eGFR values from Day -1 to Day 11 will be used for PK analysis. The eGFR determination will utilize the 4-variable MDRD equation.
- j. If QFT-G test cannot be performed, or if results are indeterminate, participants may be screened using PPD Tuberculin Test (Mantoux method), with approval of medical monitor.
- k. Confirmation of appropriate use only.
- l. HBsAb will be performed as reflex testing for any participant who is HBsAg negative but HBcAb positive ([Section 10.2.1](#)).
- m. Plasma PK sample for early termination will be collected only when the participant was terminated on \geq Day 10.
- n. If not collected on the designated collection day, collect at the next available time point when biospecimens are being collected in conjunction with a participant visit.

Pharmacokinetic Sampling Schema

Visit Identifier												
Study Day	10											
Hours Before/After Dose	0 ^a	0 ^a	0.25	0.5	1	2	4	6	8	12	16	11
Study treatment administration	X	X										
PK blood sampling	X	X	X	X	X	X	X	X	X	X	X	X
PK Urine collection ^b			X	→	→	→	→	X	→	X	→	X

Abbreviation: → = ongoing/continuous event, PK = pharmacokinetic.

- a. Predose sample collection.
- b. Urine collections during intervals of >0 and ≤6, >6 and ≤12, and >12 and ≤24 hours after dosing on Day 10. During the subsequent designated urine collection intervals ([0-6], [6-12], and [12-24] hours post dose), participants will void ALL urine produced during the designated collection interval, including a forced void at the end of the collection interval, directly into pre-weighed urine collection container. Urine samples will be analyzed using a validated analytical method in compliance with Pfizer SOPs, **only** if it is determined by the study team that there is a need to do so, based on review of PF-06651600 plasma PK results.

2. INTRODUCTION

PF-06651600 is a selective covalent inhibitor of Janus kinase 3 (JAK 3) and the tyrosine kinase expressed in hepatocellular carcinoma (TEC) family kinases and is currently under development for the treatment of alopecia areata (AA), rheumatoid arthritis (RA), vitiligo, ulcerative colitis (UC), and Crohn' Disease (CD).

2.1. Study Rationale

The primary purpose of this non-randomized, multiple dose, open-label study is to characterize the effect of renal impairment on the plasma pharmacokinetics (PK) of PF-06651600 following administration of multiple 50 mg oral doses. CCI [REDACTED]

[REDACTED]. In the first in human study, B7981001, urinary recovery ($Ae_t\%$) of PF-06651600 was low, with <8% of the dose recovered unchanged in urine, indicating that the renal pathway plays a minimal role in PF-06651600 excretion.

Evidence suggests that the PK of drugs that are not only excreted by the kidney can be affected by renal impairment through inhibition of pathways of hepatic and gut drug metabolism and transport.¹ Consequently, recent European Medicines Agency (EMA) guidelines suggest that renal impairment studies be conducted in patients with decreased renal function for nearly all small molecules, even if the drug or its active metabolite is not primarily eliminated by the kidneys.² The revised Food and Drug Administration (FDA) Draft Guidance on renal impairment studies also recommends that a PK study be conducted in participants with renal impairment when the drug is likely to be used in patients with impaired renal function.¹

PF-06651600 is intended for chronic use in patients, some of whom may have some degree of impaired renal function. Therefore, the purpose of this study is to characterize the effect of renal impairment on the plasma PK of PF-06651600. Findings from this study will be used to develop dosing recommendations so that the dose and/or dosing interval may be adjusted appropriately in the presence of renal disease.

CCI [REDACTED]

CCI [REDACTED]

[REDACTED]

[REDACTED]

[REDACTED]

[REDACTED]

[REDACTED]

[REDACTED]

[REDACTED]

CCI [REDACTED]

[REDACTED]

[REDACTED]

[REDACTED]

[REDACTED]

[REDACTED]

[REDACTED]

CCI

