3. OBJECTIVES AND ENDPOINTS

Objectives	Endpoints
Primary:	Primary:

 Part 1: To evaluate the effect of severe renal impairment on the PK of PF-06651600 following multiple oral dose administration. Part 2 (if applicable): To evaluate the effect of moderate and mild renal impairment on the PK of PF-06651600 following multiple oral dose administration. 	
 Plasma PF-06651600 PK parameters: C_{max} and AUC_{0-24}.
Secondary:	Secondary:

 To evaluate the safety and tolerability of multiple oral doses of PF-06651600 in participants with renal impairment and in healthy participants with normal renal function. 	
 Safety: treatment-emergent adverse events, clinical laboratory tests, vital signs, physical exam and ECGs.
Tertiary/Exploratory:	Tertiary/Exploratory:

 To compare additional PK parameters of PF-06651600 following administration of multiple oral doses in participants with renal impairment and in healthy participants without renal impairment. To enable exploratory research through collection of banked biospecimens, unless prohibited by local regulations or ethics committee decision. 	
 Plasma PF-06651600 PK parameters: T_{max}, AUC_{last}, CL/F, and C_{trough} on Days 8, 9, 10 and 11. Potential results from exploratory analysis of banked biospecimens (these results may or may not be generated in the context of the present study).

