Starting on Day 1, participants will receive a 50 mg QD dose of PF-06651600 up to Day 9. On the morning of Day 10, the participants will receive a 50 mg QD dose of PF-06651600 after a fast of at least 10 hours. No food will be allowed for at least 4 hours post-dose. Predose PK samples will be collected on Days 8, 9 and 10 for assessment of C_{trough} . Postdose serial blood and urine samples at specified intervals (as per [Schedule of Activities](#)) will be collected on Day 10 for 24 hours for plasma and urine PK assessments, prior to discharge from the CRU on Day 11. The eGFR value will be determined on Day -1, 2, 5, 8, and 11, and the average eGFR values from Day -1 to Day 11 will be used in PK analysis.

Safety assessments (as specified in the [Schedule of Activities](#)) will be performed during screening, prior to dosing on Day -1, Day 5 and Day 11. Only serum creatinine will be additionally assessed on S2, Day 2, and Day 8 for eGFR estimation. Physical examinations, vital sign measurements, and clinical laboratory tests will be conducted and AEs will be monitored as per [Schedule of Activities](#) to assess safety. The total participation time (ie, CRU confinement time for study procedures) for each participant in this study is approximately 11 nights/12 days (excluding screening & Follow-Up contact). Participants will have a follow-up phone call 28-35 days after last dose administration to assess for AEs.

All procedures and their timelines follow the [Schedule of Activities](#).

Age/Weight/Gender Matching Criteria:

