4.3. Justification for Dose

The study will use the PF-06651600 dose of 50 mg QD, given orally for up to 10 days. The choice of this dose is based on the highest maintenance dose of PF-06651600 currently being evaluated in Phase 3 AA and vitiligo programs. Based on the short half-life (arithmetic mean of 1.13 hours for 50 mg dose in B7981001 study), steady state is expected to be achieved within a day. However, a dosing period of 10 days was used to ensure that if there is a potential for time-dependent CYP3A4 enzyme inhibition due to PF-06651600, it can be fully observed.

Doses of PF-06651600 higher than 50 mg QD have demonstrated their safety and tolerability for up to 14 days (dose of 400 mg QD) in healthy participants (B7981001), and up to 24 weeks (dose of 50 mg QD) in participants with AA (B7931005). The dose of 200 mg QD has demonstrated safety and tolerability for up to 8 weeks in RA participants (B7981006) (Section 2.2.4.2.2). CCI

[REDACTED]

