9.4.3.1.2. Derivation of Pharmacokinetic Parameters Prior to Analysis

The plasma PK parameters for PF-06651600 following multiple dose administration will be derived from the concentration time profiles as detailed in Table 3. Actual PK sampling times will be used in the derivation of PK parameters. In the case that actual PK sampling times are not available, nominal PK sampling time will be used in the derivation of PK parameters.

Table 3. Plasma PK Parameters

Parameter	Definition	Method of Determination
AUC ₀₋₂₄	Area under the plasma concentration-time profile from time 0 to 24 hours	Linear/Log trapezoidal method.
AUC _{last}	Area under the plasma concentration-time profile from time 0 to the time of the last quantifiable concentration (C _{last})	Linear/Log trapezoidal method.
C _{max}	Maximum plasma concentration	Observed directly from data.
T _{max}	Time for C _{max}	Observed directly from data as time of first occurrence.
CL/F	Apparent clearance	Calculated as AUC ₀₋₂₄ /Dose.
C _{trough}	Pre-dose concentration	Observed from data as pre-dose concentrations on Days 8 – 10.

If urine samples need to be analyzed (See [Section 8.5.2](#)), the following urine PK parameters (Table 4) will be calculated for PF-06651600 (as data permit):

Table 4. Urine PK Parameters		
Parameter	Definition	Method of Determination
Ae ₂₄	Total amount of unchanged drug excreted in the urine over 24 hours	Sum of amount excreted for each collection period.
Ae ₂₄ %	Total amount of unchanged drug excreted in the urine over 24 hours, expressed as percent of dose	100(Ae ₂₄ /Dose)
CL _r	Renal clearance	Ae ₂₄ /AUC ₂₄

Urine PK parameters will be analyzed and summarized using descriptive statistics.

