**Table 3. Noncompartmental PK Parameters**

| Matrix | PK Parameter                 | Analysis Scale | PF-06651600 |
|--------|------------------------------|----------------|-------------|
| Plasma | AUC 0-24          | ln             | A, D        |
|        | AUC last          | ln             | D           |
|        | C max             | ln             | A, D        |
|        | T max             | R              | D           |
|        | CL/F                         | ln             | D           |
|        | C trough          | ln             | D           |
| Urine* | CL r † | ln             | D           |
|        | Ae 24             | R              | D           |
|        | Ae 24 (%)         | R              | D           |

Key: A=analyzed using statistical model, D=displayed with descriptive statistics, ln=natural-log transformed, R=raw (untransformed), \* =will be analyzed depending on Plasma PK results.

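### The results may guide the dosing interval, but no plasma parameter list includes half-life or a terminal rate constant, although the Day 10 samples would support both.

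*Protocol*

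**What the plan says.** **Purpose.** Protocol Section 2.1, repeated in SAP Section 2, says the findings will serve to "develop dosing recommendations so that the dose and/or dosing interval may be adjusted appropriately" in renal disease.

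**Parameters.** Protocol Section 3 and protocol Table 3 (Section 9.4.3.1.2) together cover AUC0-24, AUClast, Cmax, Tmax, CL/F and Ctrough for plasma. The SAP lists the same six in "Table 3. Noncompartmental PK Parameters" (Section 6.3.1) and again in SAP Table 4 (Section 8.2). None of these gives half-life, a terminal rate constant or Vz/F.

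**Vz/F.** It appears only in the Part 2 regression on eGFR (protocol Section 9.4, SAP Section 8.2), next to CL/F or CLr.

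**Sampling.** Under Section 4.1, "participants will receive a 50 mg QD dose of PF-06651600 up to Day 9". A fasted dose follows on Day 10, with serial plasma sampling for 24 hours.

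**Half-life.** Section 4.3 cites an "arithmetic mean of 1.13 hours for 50 mg dose in B7981001 study" and concludes that "steady state is expected to be achieved within a day".

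**Ctrough days.** Section 3 has Ctrough "on Days 8, 9, 10 and 11". Table 3 has it "Observed from data as pre-dose concentrations on Days 8 – 10", and Section 4.1 also ties the trough samples to Days 8, 9 and 10. SAP Table 4 lists Ctrough with no day attached.

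**The concern.** The dosing interval is one of the uses the sponsor names for the results, and how fast drug leaves plasma within the interval is information a reader would expect to see for that use. The listed parameters mostly describe the extent and peak of exposure. All participants receive the same 50 mg dose, so CL/F carries the same information as AUC0-24. A higher AUC could come from more drug reaching the circulation or from slower removal. Section 2.1 names both gut and hepatic metabolism and transport as processes that renal impairment may inhibit, so neither route can be set aside in advance.

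At stake is the interpretation of the exposure ratio, not its estimate. If the AUC0-24 ratio is below 2.0, the study ends after Part 1. A moderate rise in exposure could then be reported with no tabulated measure of elimination rate, although the samples to derive one had been drawn.

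**Working it through.** **Inputs.** Mean half-life 1.13 h (protocol 4.3); once-daily dosing, so 24 h from dose to trough (4.1); Part 2 trigger, an AUC0-24 ratio of at least 2.0 (4.1, SAP 4.2). Half-life in renal impairment is not given, so prolongations of 2, 3 and 5 times are assumed to show a range.

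**1. The plan's own inference.** Five half-lives are 5 × 1.13 = 5.65 h and seven are 7 × 1.13 = 7.91 h. Both are well under 24 h, so steady state within a day follows. Accumulation is 1/(1 − 2^(−24/1.13)) = 1.0000004, in effect 1.

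**2. Where the trough falls.** Half-lives elapsed = 24/t½; fraction remaining = 2^(−24/t½).

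| Prolongation | t½ (h) | Half-lives in 24 h | Fraction left |
|---|---|---|---|
| none | 1.13 | 21.2 | 4.0 × 10⁻⁷ |
| 2 times | 2.26 | 10.6 | 0.064% |
| 3 times | 3.39 | 7.1 | 0.74% |
| 5 times | 5.65 | 4.2 | 5.3% |

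For 1% to remain at 24 h, half-life would have to be about 3.6 h, or 3.2 times the cited value. Ctrough therefore says little about elimination unless half-life lengthens several-fold.

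**3. Why AUC and CL/F do not settle it.** For a fixed dose, AUC ratio = (bioavailability ratio)/(clearance ratio). A ratio of 2.0 arises in either of these cases:
- bioavailability doubles and clearance is unchanged: t½ stays at 1.13 h;
- clearance halves with volume and bioavailability unchanged: t½ = 2 × 1.13 = 2.26 h.

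CL/F halves in both cases. These are limiting cases. The first requires control bioavailability of at most 50%, a figure the available text does not give, and mixtures are possible.

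**4. Whether the samples can support half-life.** Assume mono-exponential decline from 1 h. The fraction of the 1 h concentration at time t is 2^(−(t−1)/t½).

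| Time (h) | t½ 1.13 h | t½ 2.26 h |
|---|---|---|
| 2 | 54% | 74% |
| 4 | 16% | 40% |
| 6 | 4.7% | 22% |
| 8 | 1.4% | 12% |

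Four scheduled samples fall on the decline before it reaches about 1%. At 8 h the two cases differ about 9-fold (12/1.4 = 8.6). The quantification limit is not stated, so how many later samples would be measurable cannot be computed.

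**5. Vz/F.** Vz/F = (CL/F)/λz, where λz is the terminal rate constant, and t½ = ln 2/λz. The Part 2 regression thus presupposes a quantity that neither document lists or defines. That regression is planned only if Part 2 is run.

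**6. Ctrough days.** Protocol Section 3 names four days; Section 4.1 and Table 3 name three. The additional Day 11 value is the 24 h sample after the fasted Day 10 dose. The Day 8 to 10 values follow doses given without fasting (Section 6.1.1).

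**The case against.** The strongest reply is that the information is largely there already. SAP Section 8.2 plans mean and median semi-log profiles with all renal groups on one plot, individual semi-log plots, and full concentration listings. A 9-fold gap at 8 h would be visible, and comparing the Cmax ratio with the AUC ratio gives a further hint. Where exposure at least doubles, Part 2 brings in Vz/F. Half-life then follows as ln 2 × (Vz/F)/(CL/F), with bioavailability cancelling.

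Much of this stands. A reader might infer that the trial cannot distinguish higher bioavailability from slower elimination. The documents do not support that, because the plots and listings would show slower elimination. What is missing is a tabulated, defined estimate by group. The Vz/F route does not supply it: Vz/F is in no parameter table, it is not planned for Part 1, and protocol Table 3 gives CL/F as AUC0-24 divided by dose. That is the inverse of clearance, so back-calculation fails as written.

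Three other stronger readings also fail:
- *Ctrough stands in for half-life.* Neither document presents it that way; it is one exploratory parameter among several.
- *Interval statements must rest on half-life.* Nothing in the documents supports such a rule. The drug is a covalent inhibitor (Section 2) given once daily although 24 h is about 21 plasma half-lives, and the basis for a dosing recommendation is outside this point.
- *Ctrough will be pooled over fasted and non-fasted days.* No text says so; SAP Table 4 simply does not state the day.

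It is also fair that the 1.13 h figure is a mean from an earlier study. Section 4.2 warns of nonlinear PK and time-dependent CYP3A4 inhibition, so half-life on Day 10 may differ. This limits the precision of the trough figures and is itself a reason to report half-life from this study.

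**Conclusion.** The point holds as a gap in the parameter lists. The interval is a stated use of the results, yet no elimination-rate parameter is listed, none is planned if the study stops after Part 1, and the Part 2 regression relies on a parameter left out of every table. Ctrough does not fill the gap: it falls about 21 half-lives after dosing at the cited mean, and about 11 to 4 at an assumed 2- to 5-fold prolongation. The 24 h fractions assume first-order decline, and the 2 to 8 h fractions assume mono-exponential decline from 1 h.

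The consequence is modest. The primary AUC0-24 and Cmax comparisons, the Part 2 trigger and the sampling are unaffected. The mismatch in Ctrough days is minor, because the Day 11 sample is drawn in any case, but the three protocol sections should agree.

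**What to change.** - Add the terminal rate constant, half-life (with the number of points used) and Vz/F to protocol Table 3 and SAP Tables 3 and 4. Derive them from the Day 10 profile and summarise them by renal group from Part 1 on, beside CL/F. Correct the CL/F formula in protocol Table 3 at the same time.
- Where the terminal phase cannot be estimated, code the value NC under SAP Section 7.3.
- Reconcile the Ctrough days in protocol Sections 3, 4.1 and 9.4.3.1.2. State in the SAP that Ctrough is summarised by day, with the Day 11 value, which follows the fasted dose, shown separately.

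The cost is table wording in both documents and a few extra output columns. The parameters come from the same noncompartmental analysis, with no added samples or visits. The downside is that a few participants may have NC values.
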